- Per protocol set: All participants in the Full Analysis set who are deemed to have no major protocol violations that could interfere with the objectives of the study.

ADVERSE EVENTS

Definitions

An adverse event (AE) is any unfavourable and unintended sign, symptom, syndrome or illness that develops or worsens during the period of observation in the study.

An AE does include a/an:

1. Exacerbation of a pre-existing illness.
2. Increase in frequency or intensity of a pre-existing episodic event or condition.
3. Continuous persistent disease or symptoms present at baseline that worsen following the start of the study.

The following are recognised complications related to chronic haemodialysis and will be recorded on the CRF, but do not need to be reported separately on an AE/Serious Adverse Event (SAE) form:

- Related to dialysis: fistula bruising, dizziness, cramps, hypotension, minor bleeding.
- Hospital admission for vascular access, acute coronary syndromes, arrhythmias, stroke, pneumonia and infections.
- Death.

An AE does not include a/an:

1. Medical or surgical procedure (e.g., surgery, endoscopy, tooth extraction, transfusion); however, the condition that led to the procedure is an AE.
2. Pre-existing disease or conditions present or detected at the start of the study that did not worsen.
3. Situations where an untoward medical occurrence has not occurred (e.g., hospitalisations for cosmetic elective surgery, social and/or convenience admissions).
4. Disease or disorder being studied, or sign or symptom associated with the disease, or disorder unless more severe than expected for the participant's condition.
5. Overdose of concurrent medication without any signs or symptoms.

A SAE is any AE occurring following study mandated procedures, directly related to the treatment or intervention that results in any of the following outcomes:

1. Death.
2. A life-threatening AE.
3. Inpatient hospitalisation or prolongation of existing hospitalisation.
4. A disability/incapacity.
5. A congenital anomaly in the offspring of a participant.

Important medical events that may not result in death, be life-threatening, or require hospitalisation may be considered a SAE when, based upon appropriate medical judgment, they may jeopardize the patient or participant and may require medical or surgical intervention to prevent one of the outcomes listed in this definition.

All AEs will be assessed for seriousness, expectedness and causality:

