A distinction is drawn between serious and severe AEs. Severity is a measure of intensity, whereas seriousness is defined using the criteria above. Hence, a severe AE need not necessarily be serious.

Causality

Not related or improbable: a clinical event including laboratory test abnormality with temporal relationship to study intervention administration which makes a causal relationship incompatible or for which other treatments, chemicals or disease provide a plausible explanation. This will be counted as "unrelated" for notification purposes.

Possible: a clinical event, including laboratory test abnormality, with temporal relationship to study treatment/intervention administration which makes a causal relationship a reasonable possibility, but which could also be explained by other interventions, chemicals or concurrent disease. This will be counted as "related" for notification purposes.

Probable: a clinical event, including laboratory test abnormality, with temporal relationship to study treatment/intervention administration which makes a causal relationship a reasonable possibility, and is unlikely to be due to other interventions, chemicals or concurrent disease. This will be counted as "related" for notification purposes.

Definite: a clinical event, including laboratory test abnormality, with temporal relationship to study treatment/intervention administration which makes a causal relationship a reasonable possibility, and which can definitely not be attributed to other causes. This will be counted as "related" for notification purposes.

With regard to the criteria above, medical and scientific judgment shall be used in deciding whether prompt reporting is appropriate in that situation.

Reporting of adverse events

Participants will be asked to contact the study site immediately in the event of any SAE. All AEs will be recorded and closely monitored until resolution, stabilisation, or until it has been shown that the study intervention is not the cause. The CI shall be informed immediately of any SAEs and shall determine seriousness and causality in conjunction with any treating medical practitioners.

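### The SAE definition requires direct relatedness to the intervention, which is narrower than the causality scale and the REC reporting rules that depend on it

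*Combined protocol and SAP*

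**What the plan says.** All the relevant text is in the protocol's Adverse Events section.

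- **Definitions, SAE.** "A SAE is any AE occurring following study mandated procedures, directly related to the treatment or intervention that results in" one of five outcomes. Death is the first and inpatient hospitalisation the third. A further paragraph lets important medical events be considered SAEs on medical judgement, and it does not repeat the relatedness test.
- **Definitions, assessment.** "All AEs will be assessed for seriousness, expectedness and causality". The text then adds: "Severity is a measure of intensity, whereas seriousness is defined using the criteria above".
- **Definitions, no-form list.** Certain events are treated as known complications of dialysis and go on the CRF, "but do not need to be reported separately on an AE/Serious Adverse Event (SAE) form". The list includes "Hospital admission for vascular access, acute coronary syndromes, arrhythmias, stroke, pneumonia and infections" and, as a bullet of its own, death with no qualifier.
- **Causality.** There are four grades. The lowest counts as unrelated; *possible*, *probable* and *definite* count as related for notification. *Possible* is an event whose timing is one "which makes a causal relationship a reasonable possibility, but which could also be explained by other interventions, chemicals or concurrent disease". The section closes by saying that "medical and scientific judgment shall be used in deciding whether prompt reporting is appropriate in that situation".
- **Reporting of adverse events.** The CI is told at once of any SAE and determines seriousness and causality. Intervention-related SAEs go into the annual REC report, and unexpected SAEs go to the REC within stated times.
- **Study Intervention Related SAEs.** The REC report covers an unexpected SAE judged directly related, or suspected to be related. The CI's action step, with a 7-day limit, says only that the event is deemed related.

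**The concern.** Seriousness and relatedness are normally separate judgements: the first looks at the outcome, the second at the cause. Here the definition merges them, while the later sections treat them as separate. The same event can then be related for notification under Causality and yet not be an SAE under Definitions.

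The steps at stake are immediate notification of the CI and the two REC routes (annual and within 7 days). All are worded for SAEs. Two members of the study team could classify the same death or admission differently, and each could point to the text. This is a question of safety oversight and does not bear on the analysis of CRP or cytokines.

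**Working it through.** The documents give no figure to reproduce here. The check is to set the wordings side by side and follow one event through them.

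| Place | What it requires |
|---|---|
| Definitions, SAE | Direct relatedness plus a listed outcome |
| Definitions, important medical events | Medical judgement; no relatedness test stated |
| Causality | *Possible* or above counts as related for notification |
| Reporting, CI notification | Any SAE |
| Reporting, annual REC report | SAEs that are intervention-related |
| Study Intervention Related SAEs, lead sentence | Directly related, or suspected to be related |
| Study Intervention Related SAEs, CI action step | Deemed related |

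**One event.** Take a participant who dies during the 6 weeks, with a cause that could be the supplement or concurrent disease.

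1. *Causality grade.* The event fits *possible*, so it counts as related for notification. So do three of the four grades; *possible* is the lowest of the three and the one that direct relatedness does not clearly cover.
2. *SAE status.* Death is a listed outcome. But an event with a plausible alternative explanation is not clearly directly related, and the protocol does not define that term. Read literally, the event is not an SAE.
3. *CI notification.* The duty to inform the CI at once is worded for SAEs, so it need not apply.
4. *REC reporting.* The annual and the 7-day routes are also worded for SAEs, so they need not apply either.
5. *What still applies.* The death is recorded on the CRF. All AEs are assessed for causality and followed until resolved, stable or shown not to be caused by the intervention. The CI is responsible for all AE reporting, and judgement on prompt reporting is available.

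**Internal signs that the clause does not fit.**

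- The CI determines causality after being told of an SAE. If causality is part of being an SAE, it has to be judged before the notification that starts that judgement.
- A report of intervention-related SAEs presupposes unrelated ones, which the definition excludes for the five listed outcomes.
- Participants are asked to contact the site at once about any SAE. They cannot first judge direct relatedness.
- The statement that seriousness follows the criteria above does not say whether those criteria include the relatedness clause.

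**The no-form list.** Death is SAE outcome 1 and also appears on this list; the listed admissions overlap outcome 3. No sentence says what happens to the form exemption when the supplement is suspected.

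**Exposure.** 15 participants × 6/52 years = 1.73 person-years. For every 1 event per person-year, about 1.73 events would be expected in the whole study. The documents give no rates for deaths, admissions or the share graded *possible* or above.

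**The case against.** The best defence is that the procedures do not use direct relatedness as a gate. The CI is informed first and judges causality second, the annual report speaks of intervention-related SAEs, and Causality states plainly which grades count as related. Together these favour an outcome-based reading, with one stray clause in the definition. That is a fair account of what was probably intended, and a sensible team might work that way. It does not remove the clause, and no sentence says that the later sections prevail.

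The safeguards are also real. They ensure that the event is recorded, assessed and followed. None of them requires immediate CI notification or REC reporting of an event outside the SAE definition; judgement on prompt reporting is a discretion.

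Three stronger readings are tempting, and the documents do not support them.

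- A reader might infer three different relatedness thresholds. *Possible* is described as a reasonable possibility, which may be the same level as suspected to be related. The protocol never maps one to the other, so the firm conflict is between one narrow clause and the broader triggers.
- A reader might infer that the REC rule for suspected SAEs has nothing to act on. That overlooks the important-medical-event paragraph, under which a suspected event can still be an SAE.
- A reader might infer that deaths and the listed admissions are exempt from reporting. The list waives a separate form only. It does not waive CI notification or REC reporting, the REC route uses the HRA's own form, and the lead-in can be read as limiting the list to events attributed to dialysis.

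**Conclusion.** The point stands as a conflict of wording. The SAE definition is narrower than the causality scale and the REC rules built on it. On a literal reading, a death or admission graded *possible* can fall outside immediate CI notification and both REC routes, though it would still be recorded, assessed and monitored. The conclusion assumes only that *directly related* does not clearly include an event with another plausible explanation. The silence of the no-form list on suspected events is secondary and matters mainly because of the definition.

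Its size in events cannot be stated. Exposure is 1.73 person-years and any count would rest on rates that the documents do not give. A reader might infer that reports will in fact be missed; the text shows only that they could be. The primary outcome and its analysis are not affected. The correction is still worth making, because it concerns deaths and admissions and is cheap.

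**What to change.** In one protocol amendment:

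1. Delete the direct-relatedness clause from the SAE definition. Seriousness then rests on the five outcomes and the important-medical-event paragraph, and relatedness is judged only under Causality. Say that the criteria for seriousness mean these two elements.
2. Under Study Intervention Related SAEs, state that suspected to be related and deemed related both mean *possible*, *probable* or *definite*, as Causality already has it for notification.
3. Remove death from the no-form list, and state that the form exemption does not apply to a listed event graded *possible* or above.
4. Say separately whether expected, unrelated listed admissions need immediate CI notification. Keeping them CRF-only waives the form and not the notification, and without the relatedness clause they would meet the SAE definition.

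The cost is the amendment itself and a small number of extra forms and CI notifications among 15 participants followed for 6 weeks. That number cannot be fixed from the documents. No change to the sample size, endpoints or analysis is needed.

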Title	Effect of immuno-nutrition on systemic inflammation in people receiving haemodialysis: a pilot study.
Acronym	
Short title	Immuno-nutrition in haemodialysis
Chief Investigator	[name]
Objectives	
 1. To investigate whether provision of an immuno-nutrition supplement decreases systemic inflammatory status in people on haemodialysis. 2. To investigate the effect of an immuno-nutrition supplement on biochemical blood variables, body composition, dietary intake and muscle strength in people on haemodialysis.
Study Configuration	Single-centre, non-randomised, interventional pilot study.
Setting	Secondary care
Sample size estimate	As a pilot study power calculations are not appropriate
Number of participants	15
Eligibility criteria	
Inclusion criteria:
 
 • CRP level >5 mg/L. • Age: ≥ 18 years (no upper age limit). • At least three haemodialysis sessions per week for ≥ 3 hours using a biocompatible dialyser. • Able to give informed consent. 
Exclusion criteria:
 
 • Treatment with drugs that cause immunosuppression. • Non-English speakers or those with special communication needs. • Pregnancy, breast feeding or intending pregnancy. • Expected survival <6 months. • Hospitalisation at the time of screening. • Known intolerance or allergy to oral nutritional supplement (or isolated ingredients). • Pre-dialysis serum potassium >5.0 mmol/L. • Unable to provide informed consent.

Description of interventions	Dietitian supervised nutritional support with an immuno-nutrition supplement (Oral Impact®, Nestle)
Duration of study	Duration of individual study participation: 6 weeks. Overall study duration: 3 months.
Methods of analysis	To compare baseline versus final evaluations, a Wilcoxon test or paired t-test will be used in the case of dimensional variables, and McNemar test in the case of categorical variables. Inter-group comparisons will be performed using a Mann-Whitney test or Student t-test for continuous variables and χ^2 test or Fisher's exact test for categorical variables. A p value <0.05 will be considered to have statistical significance.

ABBREVIATIONS

AE	Adverse Event
BMI	Body Mass Index
CI	Chief Investigator
CRF	Case Report Form
CRP	C Reactive Protein
GCP	Good Clinical Practice
HGS	Handgrip strength
NHS	National Health Service
ONS	Oral Nutritional Supplement
PIS	Participant Information Sheet
REC	Research Ethics Committee

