15 participants will be recruited from the Renal Dialysis Unit at the Royal Derby Hospital. Potential participants will be approached by the clinical care team (which may include members of the research team) with reference to the inclusion and exclusion criteria. Each eligible participant will be given a Participant Information Sheet (PIS) and a minimum of 24 hours to consider whether they wish to participate in the study. At this time, the PIS will be discussed with them, any questions answered, and informed consent will be obtained by one of the investigators if they are willing to enter the study.

It will be explained to the potential participant that entry into the study is entirely voluntary and that their treatment and care will not be affected by their decision. It will also be explained that they can withdraw at any time. In the event of their withdrawal, it will be explained that their data collected so far cannot be erased and we will seek consent to use the data in the final analyses where appropriate.

If needed, the hospital interpreter and translator services will be available to assist with discussion of the study, the PIS, consent form, and be available for the duration of the study if required. The consent form and PIS will not be available printed in other languages.

Eligibility criteria

Inclusion criteria:

- CRP level >5.0 mg/L.
- Age: ≥ 18 years (no upper age limit).
- At least three haemodialysis sessions per week for ≥ 3 hours using a biocompatible dialyser.
- Able to give informed consent.

Exclusion criteria:

- Treatment with drugs that cause immunosuppression.
- Non-English speakers or those with special communication needs.
- Pregnancy, breast feeding or intending pregnancy.
- Expected survival <6 months.
- Hospitalisation at the time of screening.
- Known intolerance or allergy to ONS (or isolated ingredients).
- Pre-dialysis serum potassium >5.0 mmol/L.
- Unable to provide informed consent.

Participant Withdrawal

Participants will be withdrawn from the study if they:

- Withdraw their consent at any time.
- Become pregnant.
- Receive a kidney transplant.
- Do not adhere to the intervention; defined as $<50\%$ of the provided immuno-nutrition supplement being consumed.

Participants do not have to provide a reason for withdrawal of consent. Participants will also be withdrawn if it is deemed unsafe or is found to be impossible to proceed in the opinion of the investigators.

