Participants may be withdrawn from the study either at their own request or at the discretion of the Investigator. The participants will be made aware that this will not affect their future care. Participants will be made aware (via the PIS and consent form) that should they withdraw the data collected to date cannot be erased and may still be used in the final analysis.

Participants will not be replaced if they withdraw from the study.

Informed consent

The process for obtaining participant informed consent will be in accordance with the Research Ethics Committee (REC) guidance, Good Clinical Practice (GCP) and any other regulatory requirements that might be introduced. The investigator or their nominee and the participant shall both sign and date the consent form before the person can participate in the study.

The participant will receive a copy of the signed and dated consent form and the original will be retained in the Study records. A second copy will be filed in the participant's medical notes and a signed and dated note made in the notes that informed consent was obtained for the study. The decision regarding participation in the study is entirely voluntary. The investigator or their nominee shall emphasize to them that consent regarding study participation may be withdrawn at any time without penalty or affecting the quality or quantity of their future medical care, or loss of benefits to which the participant is otherwise entitled. No study-specific procedures will be done before informed consent has been obtained.

The investigator will inform the participant of any relevant information that becomes available during the course of the study and will discuss with them whether they wish to continue with the study. If applicable they will be asked to sign revised consent forms.

If the consent form is amended during the study, the investigator shall follow all applicable regulatory requirements pertaining to approval of the amended consent form by the REC and use of the amended form (including for ongoing participants).

STUDY REGIMEN

Once participants have given their informed consent, they will be advised to take **daily** one sachet (74 g) of the immuno-nutrition supplement (Oral Impact®, Nestle) dissolved in 125 ml of water and will be followed-up for 6 weeks.

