Blood samples will be taken at the Renal Dialysis Unit and transferred to the local NHS laboratory (which is serviced and managed according to national UKAS standards and governance frameworks) at the Royal Derby Hospital for routine biochemistry and

haematology testing. These samples will be labelled according to NHS requirements. No DNA or RNA extraction will occur as part of this study.

STATISTICS

Statistical analyses will be performed using SPSS version 28.0. Data will be presented as mean \pm standard deviation, median (interquartile range), or percentages, as appropriate. To compare baseline versus final evaluations, a Wilcoxon test or paired t-test will be used in the case of dimensional variables, and McNemar test in the case of categorical variables. Intergroup comparisons will be performed using Mann-Whitney test or Student t-test for continuous variables and χ^2 test or Fisher's exact test for categorical variables. An alpha error of less than 0.05 will be judged to be significant. All data will be analysed on University of Nottingham computers and backed up regularly.

Sample size and justification

A formal power calculation is not appropriate for this pilot study design, and consequently, the sample size has been selected on a pragmatic basis. We will aim to recruit 15 participants in total.

Procedures for missing, unused and spurious data

All missing data will be explained. If a space on the Case Report Form (CRF) is left blank because the procedure was not done or a question was not asked, "N/D" will be recorded. If the item is not applicable to the individual case, "N/A" will be recorded. All entries will be printed legibly in black ink. If any error is made in data entry, to correct the error, a single straight line will be drawn through the incorrect entry and the correct data entered above it. All such changes will be initialled and dated. Errors will not be erased or altered by any other method. For clarification of illegible or uncertain entries, the clarification will be printed above the item, initialled and dated. Correction fluid will not be used.

Definition of populations analysed

The study will analyse the following populations:

- Safety set: All participants who underwent at least one study session.
- Full Analysis set: All participants, who participated in at least one study session and for whom at least one post-baseline assessment of the primary endpoint is available.

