In the event of a pregnancy occurring in a study participant or the partner of a study participant, monitoring shall occur during the pregnancy and after delivery to ascertain any study related AEs in the mother or the offspring. Where it is the partner of a study participant, consent will be obtained for this observation from both the partner and her medical practitioner.

All intervention related SAEs will be recorded and reported to the REC as part of the annual reports. Unexpected SAEs will be reported within the timeframes to the REC as stated below. The CI shall be responsible for all AEs reporting.

Study Intervention Related SAEs

A SAE that is unexpected in its severity and seriousness and deemed directly related to or suspected to be related to the study intervention shall be reported to the REC that gave a favourable opinion as stated below.

The event shall be reported immediately of knowledge of its occurrence to the CI.

The CI will:

- Assess the event for seriousness, expectedness and relatedness to the study intervention.
- Take appropriate medical action, which may include halting the study and inform the Sponsor of such action.

- If the event is deemed related to the study treatment or intervention, shall inform the REC using the reporting form found on the HRA web page within 7 days of knowledge of the event.
- Shall, within a further eight days, send any follow-up information and reports to the REC.
- Make any amendments as required to the study protocol and inform the REC as required.

Participant removal from the study due to adverse events

Any participant who experiences an AE may be withdrawn from the study at the discretion of the Investigator. The overall risk of an AE directly connected to the study is low.

ETHICS COMMITTEE AND REGULATORY APPROVALS

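### Withdrawal from the study for any adverse event, or at discretion, removes the only post-baseline CRP and cytokine values, and where inflammatory episodes would persist to week 6 this pushes the paired change downwards

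*Combined protocol and SAP*

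**What the plan says.** The Synopsis describes a "Single-centre, non-randomised, interventional pilot study". Blinding is not mentioned, and in a single-arm study the investigator knows what the participant is taking.

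Three statements govern removal:

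- Participant removal from the study due to adverse events, permissive: "Any participant who experiences an AE may be withdrawn from the study at the discretion of the Investigator". There is no limit by seriousness, cause or timing.
- Participant Withdrawal, general discretion: "Participants may be withdrawn from the study either at their own request or at the discretion of the Investigator". No adverse event is needed.
- Participant Withdrawal, mandatory: "Participants will also be withdrawn if it is deemed unsafe or is found to be impossible to proceed in the opinion of the investigators". The same list withdraws participants who consume less than half of the supplement.

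All three refer to leaving the study. Nowhere is stopping the supplement distinguished from ending data collection, and no assessment after withdrawal is planned.

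An adverse event is "any unfavourable and unintended sign, symptom, syndrome or illness that develops or worsens during the period of observation in the study", which covers intercurrent infection. Data collection procedures schedules CRP and cytokines at baseline and 6 weeks only; the weekly sample is for potassium. The Full Analysis set is limited to participants "for whom at least one post-baseline assessment of the primary endpoint is available". Withdrawn participants are not replaced. The missing-data section says that missing data will be explained and then deals with how the CRF is completed.

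**The concern.** The primary outcome is systemic inflammation, and infection or other inflammatory illness is both an adverse event and a cause of raised CRP and cytokines. A removal rule triggered by adverse events can therefore be related to the value that would have been seen at week 6. With one group and a paired test, no control arm undergoes the same selection and cancels it.

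Each such removal deletes a pair that would tend to show a rise or a smaller fall, so the remaining pairs look more favourable to the supplement. With 15 participants, two or three lost pairs matter, and the result is meant to inform the design of a randomised trial.

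**Working it through.** **The chain in the text.** Withdrawn before week 6 → no week-6 CRP or cytokines → no post-baseline primary value → outside the Full Analysis set. The Per protocol set is a subset of the Full Analysis set, so it does not recover them. Permission to use data already collected does not help, because only the baseline value exists.

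**The plan's own figure.** There is none to reproduce. The sample size of 15 is pragmatic, and no effect size, SD, event rate or dropout rate is given. For scale, 15 complete pairs detect a standardised change of (1.96 + 0.84)/√15 = 0.72 with 80% power at two-sided 0.05 (the plan does not state sidedness).

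**Size of the shift.** All inputs are assumptions: no supplement effect; an episode multiplies CRP by 4; probability q of an episode on treatment that is still active at week 6; a share w of those affected withdrawn first. Among those who remain, the proportion with an episode is q(1 − w)/(1 − qw), so

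shift in mean log CRP change = ln 4 × [q(1 − w)/(1 − qw) − q], with ln 4 = 1.386.

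- q = 0.10, w = 0.5: 1.386 × (0.05/0.95 − 0.10) = −0.066, a 6% fall.
- q = 0.25, w = 0.5: 1.386 × (0.125/0.875 − 0.25) = −0.149, a 14% fall.
- w = 1: the shift is −1.386q.

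The last two columns below come from simulation: 20,000 trials per cell, n = 15, the same q at baseline, residual SD of log change 0.6, one-sample t-test on the log change.

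| q | Shift, half withdrawn | Shift, all withdrawn | False significant fall, half | False significant fall, all |
|---|---|---|---|---|
| 0.10 | −6% | −13% | 4.2% | 7.4% |
| 0.15 | −9% | −19% | 5.2% | 10.9% |
| 0.20 | −12% | −24% | 5.8% | 15.4% |
| 0.25 | −14% | −29% | 7.2% | 20.5% |

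With nobody withdrawn, the change is 0% and the false-fall rate is about 2.5%.

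**Does the net sign hold?** Take q = 0.20 and a fivefold rise (ln 5 = 1.609), and let the exclusion of hospitalised patients remove a share h of baseline episodes. The baseline proportion becomes 0.20(1 − h)/(1 − 0.20h).

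| Baseline episodes excluded | None withdrawn | Half withdrawn | All withdrawn |
|---|---|---|---|
| None | 0% | −13% | −28% |
| Half | +15% | 0% | −16% |
| All | +38% | +20% | 0% |

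For the middle row the baseline proportion is 0.10/0.90 = 0.111. The entries are 1.609 × (0.20 − 0.111) = +0.143, 1.609 × (0.111 − 0.111) = 0 and 1.609 × (0 − 0.111) = −0.179. In every row, going from none to all withdrawn lowers log change by 1.609 × 0.20 = 0.322. The downward shift is therefore constant while the net result is not.

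**Two further checks**, by simulation with the same 20% and fivefold inputs (assumed median CRP 8 mg/L, between-person SD 0.8 and within-person SD 0.5 on the log scale). If on-treatment episodes have all resolved by week 6, withdrawal adds nothing: the change is about −28% at every withdrawal rate, caused by the baseline episodes. If the CRP >5 mg/L criterion is applied, the change is −19% with nobody withdrawn, −29% with half and −41% with all. The first of these is regression to the mean together with selected baseline episodes.

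**The case against.** A reader might infer that the rule makes a spurious fall certain. The documents do not support that. The rule is permissive, and nothing indicates routine removal for infection. Admissions for pneumonia and infection are listed as recognised complications of dialysis, recorded on the CRF without a separate form. The definition also leaves out "Disease or disorder being studied, or sign or symptom associated with the disease, or disorder unless more severe than expected", so a raised CRP alone is arguably not an adverse event. No interim CRP is scheduled on which to select, and withdrawals for taste, gastrointestinal intolerance or potassium need not be related to CRP. All of this stands: the bias is possible, not built in.

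A reader might also infer that baseline episodes stay in while treatment episodes go out. That is only partly so. Hospitalisation at screening is an exclusion, so only non-hospitalised episodes remain at baseline, and the net sign is open, as the second table shows.

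A third inference would be that removal contradicts adverse event follow-up, or ends it. It does not. "All AEs will be recorded and closely monitored until resolution, stabilisation", or until the intervention has been shown not to be the cause, and no exception is made for people who have left the study. Similarly, the removal statements are not strictly contradictory: one is mandatory and two are permissive. They do set different thresholds, and rewording the adverse event section alone would achieve nothing while the general discretion stands.

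What the objection does not touch is the loss of the primary value on withdrawal, and the direction of the shift where inflammatory episodes persist to week 6.

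**Conclusion.** The point holds in a limited form. Adverse event or discretionary withdrawal before week 6 removes the participant from the primary analysis, with no replacement and no analysis to show what the loss does. If those withdrawn include people whose inflammation would still be active at week 6, the paired change moves downwards. Under the assumptions shown, that shift is about 6–14% with half withdrawn and 13–29% with all withdrawn. The actual size and the net sign cannot be known from the documents. Any fall due to regression to the mean from the CRP entry criterion is a separate matter and would remain. The change is worth making because it is specific and cheap and removes a source of selection that an uncontrolled pilot cannot otherwise detect.

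**What to change.** - Reconcile the two Participant Withdrawal statements with the adverse event removal section, so that stopping the supplement (the investigator's decision, unchanged) is separate from leaving data collection.
- Unless consent is withdrawn or assessment is impossible, take the scheduled week-6 CRP and cytokine samples in every participant and analyse them in the Full Analysis set. Its definition already admits them once the sample exists.
- Do not use a sample from the stopping visit as the primary value: it could catch CRP during the acute episode and bias the change upwards.
- Report the number, timing and reason for each removal, and intercurrent infections at baseline and week 6.
- Add a sensitivity analysis for missing week-6 values.
- Leave safety monitoring after stopping to the investigators.

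The cost is protocol wording and a few week-6 blood sets, usually obtainable because participants attend dialysis at least three times a week. The downside is that the estimate will include some people who stopped the supplement, so it may be somewhat smaller and noisier.
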